# 2.4.1 Enrollment Process

As part of the overall risk management plan (see below for additional provisions), enrollment will proceed as follows:

- The study will start with dose group A1 (HIV-negative, IGRA-negative; 0.1 mg per dose).
  - The enrollment procedure comprises the following steps:
  - The first subject will be dosed with vaccine (Day 1) open-label, observed for 1 hr, and examined on Day 3 (~48 hr post-dosing). If there have been no significant safety-related events, enrollment will proceed.
  - For the remaining 15 subjects in the dose group, treatment will be assigned by randomization for A1-A3 and will be open label for A4, B1 and B2
  - A maximum of five subjects may be randomized per calendar day.
- After all subjects in the dose group have completed Study Day 7 follow-up visit, all available data will be reviewed by the Dose Review Committee (DRC; see Section 7.7 for details). Escalation to the next dose level will be contingent on their recommendation.
- If the DRC approves dose-escalation, then enrollment in dose group A2 will commence, using the same process as described for group A1. Similarly, a dose-escalation review will be conducted after all group A2 subjects complete Day 7 follow-up visit; and, if approved, enrollment in dose group A3 will proceed as detailed above.
- After all subjects in dose group A3 have completed the 7d safety evaluation after dose #3 the available safety data including injection site reactions will be conducted by the DRC, supplemented by the PI and, possibly, additional consultants with relevant expertise (e.g., immunology, tuberculosis).
- If the DRC concludes that the A3 dose level of 1 mg is safe then dose group A4 (HIV-negative, IGRA-positive) will be enrolled and administered the 1 mg dose level. If the DRC determines that the 1 mg dose is not safe then they will recommend one of the lower dose levels from A1 or A2 for A4. Subjects may be enrolled as available, up to a maximum of four subjects per calendar day.
- The dose selection review will also assess the vaccine's safety with regard to its administration to HIV-positive subjects. Progression to Part B will be contingent on that review and on the availability of resources.
- Dose group B1 will comprise HIV-positive, IGRA-negative subjects scheduled to receive DAR-901 at the same dose as the A4 cohort. This dose group will be enrolled using the same dose procedure steps detailed above for dose group A4.

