# 2.9 Schedules of Study Events

Table 2-2. Schedule of Study Events – Screening Through Day 74

Event / Evaluation  Dose #			#1							#2				
Day 	≤-28		1		+3 	+5 	+7 ⁵	+10 to		53-67	7	+3,54	+7	+10 to
Hour		Pre	0	1	]			+28 	Pre	0	0.5			+28 
Informed Consent	Х													
Medical History	Х													
Physical examination 	Х	Х												
Vital signs	Х	Х		Х	$X^3$		Х		Х		Х		Х	
Injection Site Assessment 					X3		Х		Х				Х	
Phone Contact					Х	Х		Х				Х		Х
Safety Laboratory Tests	Х	X 							Х					
HIV Monitoring Tests 	Х	X 							Х					
Urinalysis	Х								Х					
Pregnancy test (F only)	Х	Х							Х					
IGRA test, Chest X-ray 	Х													
Serology 	Х													
Immunogenicity Studies		X 							Х					
Dose administration			Х							Х				
Monitoring AE & Con Med		From Screening to End of Study Visit												

 "+7" indicates visit to be performed 6 to 8 days after actual day of dosing.

 Physical exam includes weight and, at screening only, height.

<sup>1 For details of study evaluations see Section 10.

<sup>2 Day is relative to the calendar day of the first injection of study drug, designated Day 1; time (Hour) is relative to time of injection, designated 0 hr. "Pre" indicates within 2 hr prior to injection.

 $\frac{3}{4}$  Day 3 visit only for first subject in each cohort. All other subjects will be contacted by phone on Day 3.

<sup>4 "+3", "+5", "+10 to +28" – indicates phone contacts for adverse event monitoring, including injection site

reactions, to be performed on days 3 and 5 post-dosing and at least twice weekly through day 28 post-dosing.

<sup>7 Assessment of injection site area comprises a structured examination of the injection site and measurements of any reaction (see Section 12.5).

<sup>8 HIV monitoring tests – HIV viral load, CD4 counts; to be performed only on HIV-positive subjects

<sup>9 IGRA will be performed on all subjects. All IGRA positive subjects will have a chest x-ray; see Section 2.4.2 for provisions regarding preventive therapy in those subjects.

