Event Day /Evaluation 	Vol (mL)	Scrn	1	53-67	113-127	+7	+28	+56	EOS 293-307	Approx Total Vol (mL)
Dose #			#1	#2	#3					
Safety Lab Tests	15	Х	Х	Х	Х		х		Х	78
HIV Monitoring Tests	10	Х	Х	х	Х		х			50
Pregnancy test (F only) 		Х	Х				х			0
Immunogenicity (cells)	40		Х	Х	Х	Х	X	Х	Х	280 
Immunogenicity (serum)	5		Х	х	Х	Х	х	Х	Х	35 
RNA expression	3		Х	х		Х			Х	12
Serology (Hep B, C, HIV)	10	Х								10
Total mL blood drawn		35	73	73	70	48	70	45	51	465 

 <sup>19 The volumes shown are estimates; final volumes may vary, but will not be more than 15% greater than shown.
  For details of study evaluations see Section 10.
  Pregnancy test does not require additional blood volume.
 Limit of two immunogenicity assays for HIV positive subjects in cohorts B1 and B2 reduces total volume of phlebotomy by 225 mL to 237 mL

DAR-901	
Protocol DAR-901-MDES, Version 4.1	

Page 14 of 75 Date: 30 March 2015

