### Table 2-5. Overall Study Timeline

Cohort	A1	A2	A3	A4	B1	B2
HIV status	Neg	Neg	Neg	Neg	Pos	Pos
IGRA status	Neg	Neg	Neg	Pos	Neg	Pos
Dose Level	0.1 mg	0.3 mg	1 mg	TBD	TBD	TBD
Study Week						
1	Dose #1					
2	7d Visit					
3	Safety review					
4		Dose #1				
5		7d Visit				
6		Safety review				
7			Dose #1			
8			7d Visit			
9	Dose #2					
12		Dose #2				
15			Dose #2			
17	Dose #3					
20		Dose #3				
23			Dose #3			
24						
25		_		_		
26			Dose Safety Rev	view		
27			2000 00.00, 100	Dose #1	Dose #1	
28				7d Visit	7d Visit	Dose #1
29				Safety review	Safety review	2000 // 1
30				ouldly forfion	culoty forlow	
35				Dose #2	Dose #2	
36				2000 //2	2000 //2	Dose #2
38						DOOD IFE
41	End of Study					
43				Dose #3	Dose #3	
44		End of Study				Dose #3
46						
47			End of Study			
52						
55						
67				End of Study	End of Study	
68						End of Study

TBD, dose for A4, B1, and B2 to be determined based on safety review; see text for details.

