- Erythema and/or edema seen at the majority of injection sites beginning 1 to 2 days postinjection and typically lasting for 4 to 6 days.
- Induration seen at the majority of injection sites, typically with delayed onset at the sites injected for doses 1, 2, and 3 (days 0, 14, and 28, respectively), with induration first noted at the exams on day 47 to 49. For doses 4 and 5 (days 42 and 56, respectively), the onset of induration of induration was more rapid and was noted as early as 1 week post-injection. Thus, as the study progressed, induration was frequently noted at locations separate from the most recent injection site. The size of the induration was typically 1 to 10 mm; occasional larger induration reactions appeared to represent the confluence of induration at two adjacent injection sites.
- Ulceration a subset of injection sites developed ulceration, which was described as minimal or moderate except in three animals where ulceration was described as severe at one to three injection sites each.
  - Overall, 20 (33%) of 60 test-article animals had ulceration at one or more injections sites during the course of the study. Most ulcerations resolved by the time of sacrifice.
  - Among 40 animals sacrificed at day 60, 4 (10%) had ulceration at one to four injection sites; in three of the four animals the sites from dose 1 or 2 (day 0 and 14, respectively) were ulcerated.
  - Among the 20 animals sacrificed on day 70, 3 (15%) had ulceration at two or three injections sites; in all cases the involved sites represented doses 3, 4 or 5 (days 28, 42, and 56, respectively).

Minor changes in clinical pathology were noted, consistent with an inflammatory response, but none were considered adverse. Microscopic examination confirmed an inflammatory response at the injection site in animals with cutaneous ulceration.

Conclusions. Injection site reactions were observed in animals who received five (5) administrations of DAR-901 at a dose 2.5x higher than the maximum human dose proposed in Phase I dose escalation study. Most reactions were resolving at the time of necropsy. The reactions at early injection sites were delayed and were more frequent and intense after administration of multiple doses, consistent with the induction of a strong cutaneous delayed hypersensitivity response after multiple immunizations.

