### 10.4 Reporting of Safety Laboratory Tests

The results of Safety Laboratory Tests will be returned to the Investigator as quickly as possible, typically within 48 hours. Reference ranges (lower limit of normal, upper limit of normal; by sex and age, if appropriate) will be provided for all laboratory analytes.

Procedures for the investigator assessment of laboratory results are detailed in Section 12.1.5.

Procedures for the analysis of laboratory data are described in Section 14.4.

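### A3, the first 1 mg cohort, has no planned Dose Review Committee review until week 26, after all 30 of its 1 mg injections; one earlier review and one data circulation would be a cheap improvement

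*Protocol*

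**What the plan says.** Protocol Section 2.4.1 has the DRC review A1 once every subject has had the Day 7 visit after the first dose, and adds: "Escalation to the next dose level will be contingent on their recommendation". A2 follows the same pattern: "Similarly, a dose-escalation review will be conducted after all group A2 subjects complete Day 7 follow-up visit". For A3 the only review named comes after the third dose: "After all subjects in dose group A3 have completed the 7d safety evaluation after dose #3 the available safety data" go to the committee, which then settles the dose for A4 and progression to the HIV-positive cohorts.

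Table 2-5 matches. An entry "Safety review" stands in week 3 for A1 and week 6 for A2, one week after each 7-day visit. The same entry stands in week 29 for A4 and B1, again one week after their 7-day visits. A3 has its 7-day visit in week 8 and no such entry. The next review is in week 26.

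Other controls run alongside. Under Section 7.7 the DRC promptly reviews any SAE, and any dose group in which two or more subjects have a dose-limiting toxicity (DLT). Under Section 7.5.1 a subject with a DLT gets no further doses. The first subject in each cohort is seen on Day 3.

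**The concern.** A3 is the first group to receive 1 mg of a product with no earlier clinical use (Section 5.4). The committee that decides on dose has no planned look at that dose until the whole three-dose course has been given.

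First-dose data to Day 7 are a limited guide to repeat dosing. In the mouse toxicology study (Section 5.3.4: 2.5 mg, five doses, two-week intervals) reactions at early injection sites were "delayed and were more frequent and intense after administration of multiple doses". Table 5-5, footnote 1, says that reactions to the predecessor, SRL 172, were typically largest after dose 3. In Study 005 (Table 5-4, footnote b) two HIV-positive subjects withdrew for injection site reactions after dose 3.

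Section 7.7 lets the DRC advise closer monitoring, an intermediate dose level or stopping treatment in running cohorts. No planned review comes early enough to use those options during the A3 course.

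**Working it through.** **Inputs.** Ten DAR-901 subjects in each of A1, A2 and A3 (Table 2-1). Three doses each, with Dose #2 on Day 53-67 and Dose #3 on Day 113-127 (Section 2.4). Nominal dose weeks from Table 2-5: A1 1, 9, 17; A2 4, 12, 20; A3 7, 15, 23. Planned reviews: weeks 3, 6 and 26.

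**1. The plan's week 26.** Study week = start week + floor((day - 1)/7). For A3, starting in week 7:
- Dose #3, Day 113: 7 + 16 = week 23
- Dose #3, Day 127: 7 + 18 = week 25
- Latest 7-day visit, Day 134: 7 + 19 = week 26

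This reproduces the table.

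**2. DAR-901 injections given before each planned review.**

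| Review | A1 | A2 | A3 (1 mg) | Total | Repeat doses |
|---|---|---|---|---|---|
| Week 3 | 10 | 0 | 0 | 10 | 0 |
| Week 6 | 10 | 10 | 0 | 20 | 0 |
| Week 26 | 30 | 30 | 30 | 90 | 60 |

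The gap between reviews is 26 - 6 = 20 weeks. The first look at 1 mg comes 26 - 7 = 19 weeks after the first 1 mg dose. In the gap fall 90 - 20 = 70 injections, 60 of them repeat doses.

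**3. Where an earlier review fits.**
- First possible A3 Dose #2, Day 53: 7 + 7 = week 14. The review must be finished by week 13.
- A1 Dose #2 falls in weeks 8-10. Its latest 7-day visit (Day 74) is 1 + 10 = week 11, so these data are in hand.
- A2 Dose #2 falls in weeks 11-13. Its 7-day visits run from week 12 to week 14 (Day 74: 4 + 10), so these data may be partial.
- First possible A3 Dose #3 is week 23, so a circulation is due by week 22. A1 Dose #3 is finished by week 19 (Day 127: 1 + 18). A2 Dose #3 can run to week 22 (4 + 18), so complete A2 third-dose data are not assured.

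A review before Dose #2 leaves 20 of 30 (67%) of the 1 mg injections still to come. A circulation before Dose #3 leaves 10 of 30 (33%).

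**4. What the event triggers would catch.** An injection site DLT needs Grade 3 (Section 7.5.1), so Grade 2 reactions in all ten A3 vaccinees would not of themselves bring the committee together. For the two-DLT rule among ten vaccinees, P = 1 - (1 - p)^10 - 10p(1 - p)^9. At assumed true DLT rates of 10%, 20% and 30% this is 0.26, 0.62 and 0.85. The documents give no DLT rate for DAR-901.

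**The case against.** The strongest reply is that A3 is already well watched. Systemic events count as DLTs from Grade 2 if they last beyond 48 hours and are at least possibly related. Subjects keep diaries and are called twice weekly, and the investigator may stop treatment at discretion. A DRC member may also be the Medical Monitor. SRL 172 at 1 mg was given to more than 1000 adults (Section 2.4.2.2). In the DarDar trial 1.2% were discontinued by the physician for possibly or probably vaccine-related reactions (Table 5-5, footnote 5), and all reactions were considered mild or moderate. This stands, and it limits the gain. It would be wrong to infer that A3 has no oversight before week 26; what is missing is a planned committee look.

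A second reply is that the Day 7 sentence in Section 2.4.1 speaks generally of the dose group, and that the DRC Charter, which is not shown, may cover A3. But the A3 bullet names only the review after Dose #3, and Table 2-5 agrees. The lack of a higher dose does not explain the omission either, since A4 and B1 do not escalate and still have an entry (the table does not say who performs it). If an A3 review was intended, text and table need correcting.

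Some stronger readings are not supported:
- Two of the three DarDar sterile abscesses followed dose 3, which might seem to strengthen the case. Both were in people with prior TB (Table 5-5, footnote 3), and a history of active TB is excluded here.
- Three of the five Study 005 withdrawals followed a fourth dose, which this trial does not give.
- An earlier review would not solve the laboratory timing. A3's first post-vaccination draw is before Dose #2, where the pre-dose label "indicates within 2 hr prior to injection". Section 10.4 adds: "The results of Safety Laboratory Tests will be returned to the Investigator as quickly as possible, typically within 48 hours". A review before A3 Dose #2 therefore holds no A3 post-vaccination laboratory results.
- No review before A3 Dose #3 can show a third-dose reaction at 1 mg. It can show third doses at the lower levels.

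**Conclusion.** The point holds as a modest, low-cost safety improvement that should be made. It is not a fatal flaw. On the plan's own calendar all 30 A3 injections at 1 mg precede the first planned DRC look at that dose, and A3 alone among cohorts with a listed 7-day visit lacks a safety review the following week.

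The conclusion rests on Table 2-5's nominal weeks. If A1 or A2 enrolled slowly, the review that opens A3 could include some repeat-dose data. It also rests on the Charter adding no A3 review. No number of avoided reactions can be estimated from the documents. The 67% is a share of injections, not of harm. The benefit is that a pattern below the SAE and two-DLT thresholds, such as frequent Grade 2 injection site reactions, would reach the committee while dosing could still change.

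**What to change.** Add to Section 2.4.1 and Table 2-5:

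- **One DRC review of available data** after the A3 Day 7 visit, completed before the first A3 Dose #2 (by week 13). It should cover A3 post-Dose #1 data, A1 post-Dose #2 data and pre-Dose #2 laboratory results, and whatever A2 post-Dose #2 data exist. The majority approval and recommendations in Section 7.7 apply unchanged.
- **One circulation to the DRC** before the first A3 Dose #3 (by week 22). It should hold the available A1 and A2 post-Dose #3 data and A3 post-Dose #2 data, including A3 pre-Dose #2 laboratory results.

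Do not hold dosing for complete data. The cost is one meeting of the existing three-member committee and one circulation, with no new visits or samples. There is a small risk of delaying A3 Dose #2. If A2 post-Dose #2 visits are wanted in the review, the nominal slack is about one week, which is why it should work from available data. The timing of the A3 laboratory draw would need a separate change.

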# 2.4.2 Risk Management

The subjects in this Phase 1 trial are not expected to benefit from the treatment.

In addition to the staggered enrollment and dose escalation procedures detailed above, the following steps have been taken to minimize the risk of participation in this study.

# 2.4.2.1 Stratification by IGRA

As part of the screening procedures all subjects will have an IGRA to determine prior exposure to TB.

• Subjects with negative IGRA may be enrolled in the cohorts A1, A2, A3 and B1.

- Subjects with an IGRA reported as "indeterminate" (as defined by the manufacturer) will not be enrolled in the study and will be provided the IGRA result and referred to their personal physician.
- Subjects with a positive IGRA may be enrolled in cohorts A4 or B2, subject to the following conditions.
  - Prior to enrollment all IGRA-positive subjects will have chest x-ray and medical evaluation to exclude signs or symptoms of active TB.
  - Subjects currently taking preventive therapy for latent TB, or intending to start it imminently, will not be enrolled (HIV positive subjects who are IGRA positive will have all been offered preventive therapy by their primary physicians).

# 2.4.2.2 Dosing procedures

- All doses of study treatment (DAR-901, BCG, and placebo) will be prepared by a research pharmacist.
- All intradermal injections of study treatment in dose groups A1, A2 and A3will be administered by a blinded research nurse who will not participate in other clinical study activities. All evaluations will be performed by blinded study personnel not involved in preparation or administration of study treatment.
- Intradermal injections of DAR-901 in open label dose groups A4, B1 and B2 will be performed by the main study nurse
- All subjects will be observed for at least 30 minutes following all injections.
- The maximum dose is based on prior experience in >1000 adults with SRL-172, a killed mycobacterial vaccine prepared from the same strain. As noted above, there were 0.3% injection site sterile abscesses and 0.4% self-limited generalized rashes (see Table 5-5).

# 2.4.2.3 Adverse event monitoring

- At all visits subjects will be asked about adverse events and concomitant medications and a detailed injection site assessment will be performed.
- Between scheduled visits, subjects will be monitored by phone contacts twice weekly through +day 28 post-injection. Subjects will be provided a thermometer to measure body temperature and a ruler to measure injection site reactions. To assure accurate reporting at the scheduled phone calls, subjects will be provided a memory-aid diary to record findings and symptoms daily.
- Digital photographs will be obtained of injection site reactions that include skin breakdown, pustules or abscess
- Subjects whose clinical course suggests secondary complications, e.g., sterile or infected abscesses, will be asked to return to the clinic for evaluation by the investigator.
- Safety laboratory tests will be performed as detailed below. Subjects with treatment-emergent abnormalities meeting predefined toxicity grades will have study treatment discontinued (see Section 7.5.1).
- Subjects will be discontinued from study treatment (see Section 7.6.1) if they experience a doselimiting toxicity (DLT) event, either systemic, local to the injection site, or demonstrated on laboratory tests (see Section 7.5.1 for details).

# 2.4.2.4 Other risk management procedures

- For HIV-positive subjects data on compliance with anti-retroviral therapy will be collected at each visit.
- All HIV-positive subjects will have a baseline chest x-ray to exclude active tuberculosis.
- Given the exploratory nature of this study, the sample size is based not on power calculations but rather on prior Phase 1 experience indicating that cohorts of this size are the minimum required to provide sufficient data for safety, tolerability, immunogenicity, and dose response assessment for advancing the development process.

**Confidential and Proprietary** 

[name] 5/31/15 10:25 AM Deleted: Table 5-5 • The trial will be conducted in compliance with the protocol, GCP, and applicable human studies and regulatory requirements.

### 2.4.3 Study Structure

2.4.3.1 Screening through Day 74

- Table 2-2. Schedule of Study Events Screening Through Day 74,
- Screening will be done within 28 days before the first injection of study drug.
- Subjects will receive the first dose as assigned on Day 1.
- Subjects may be discharged from clinic following completion of scheduled procedures.
- Subjects will be seen in clinic for scheduled procedures 7 days after dosing.
- Subjects will be contacted by phone for adverse event monitoring, including injection site reactions, twice weekly thru +28 days after dosing.
- Dose #2 will be administered  $60 \pm 7$  days after Dose #1.
- Subjects will be seen in clinic for scheduled procedures 7 days after dosing.
- Subjects will be contacted by phone for adverse event monitoring, including injection site reactions, twice weekly thru +28 days after dosing.

### 2.4.3.2 Dose #3 through End-of-Study

- Table 2-3. Schedule of Study Events Dose #3 to End-of-Study Visit,
- Dose #3 will be administered  $120 \pm 7$  days after Dose #1.
- Subjects will be seen in clinic at 7, 28, and 56 days after dosing for scheduled procedures.
- Subjects will be contacted by phone for adverse event monitoring, including injection site reactions, twice weekly thru +28 days after dosing.
- The End-of-Study (EOS) visit, the final study event, is scheduled for  $180 \pm 7$  days after Dose #3.
- Total duration of involvement is ~330 days (11 months).

### 2.4.4 Potential protocol adjustments

The protocol is written with flexibility to accommodate the dynamic nature of Phase 1 clinical trials. An additional cohort may be enrolled, either to repeat a dose level or to administer a dose below or between the levels specified. In no event will the proposed maximum exposures be exceeded.

### 2.5 Subject selection

# 2.5.1 Inclusion Criteria – HIV-negative Subjects

To be eligible for this study, a subject must meet **all** of the following inclusion criteria:

- 1. Be age 18 to 65 years, inclusive;
- Have completed the informed consent procedure (see Section 15.3), including signing and dating the informed consent form;
- Have received BCG as documented by presence of a scar consistent with immunization or a contemporary medical record;
- 4. Have two negative ELISA assays for antibody to human immunodeficiency virus type 1 and 2 (HIV-1, HIV-2);
- 5. Female subjects must have a negative serum pregnancy test at screening and negative urine pregnancy test within 24 hr prior to each dose of study drug;
- Female subjects of childbearing potential (see Section 8.3) must agree to use effective birth control (contraception; see Section 8.3) from Screening through the treatment period and for 3 months after the last injection of study drug.

